### 5.4. Scientific Rationale for Study Design

This study will examine the effect of 16 weeks of induction dosing followed by evaluation of continuous dosing compared with PRN dosing in the maintenance period. All placebo subjects and subjects assigned to treatment with LY3074828 that have a <PASI 90 at Week 16 will receive LY3074828 300 mg SC Q8W during the entire maintenance treatment period. Subjects

with  $\geq$ PASI 90 (PRN dosing group) at Week 16 will only be dosed with LY3074828 at the baseline dose level assignment no more frequently than Q8W when disease activity level is  $<$ PASI 90, and this will continue until  $\geq$ PASI 90 is regained. The 2-year study duration will allow evaluation of the frequency of dosing a subject needs to maintain a high level PASI response.

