4.3. Exploratory Objectives

- To characterize the loss of response during the Maintenance Period (if applicable) for subjects who achieve PASI 100 at Week 16
- To characterize the loss of response during the Maintenance Period (if applicable) for subjects who achieve PASI 90 at Week 16
- To characterize the ability of retreatment (if applicable) with LY3074828 to regain PASI 100 for subjects who achieve PASI 100 response at Week 16 and experience loss of response during the Maintenance Period
- To characterize the ability of retreatment (if applicable) with LY3074828 to regain PASI 90 for subjects who achieve PASI 90 response at Week 16 and experience loss of response during the Maintenance Period
- To evaluate the efficacy of treatment with LY3074828 in inducing PASI 100, PASI 90, PASI 75, and mean PASI improvements at all time points evaluated
- To evaluate the efficacy of treatment with LY3074828 in inducing mean BSA improvements at all time points evaluated
- To evaluate the efficacy of treatment with LY3074828 in inducing sPGA 0 and sPGA 0/1 at all time points evaluated

- To evaluate the efficacy of treatment with LY3074828 in PSSI at all time points evaluated
- To evaluate the efficacy of LY3074828 on patient reported outcome measures: Psoriasis Symptom Scale, Patient Global Assessment, DLQI, and SF-36 at all time points evaluated
- To evaluate the psychometric properties of the Psoriasis Symptom Scale including validity, reliability, and responder definition
- To evaluate the relationships between LY3074828 exposure, biomarkers, and efficacy
- To evaluate the development of anti-drug antibodies for LY3074828.

5. Study Design

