5.1. Summary of Study Design

Study AMAF is a multicenter, randomized, parallel-arm, placebo-controlled trial with 4 study periods in subjects with moderate-to-severe plaque psoriasis.

[figure not shown]
Screening Period (≤4 weeks): Subjects will be evaluated for study eligibility ≤28 days before the baseline visit (Visit 2/Week 0). At the baseline visit (Visit 2), subjects who fulfill the eligibility criteria will be randomized to 1 of 4 induction treatment arms.

Induction Period (16 weeks): A double-blind, 16-week Induction Period is designed to establish the efficacy and safety of LY3074828 administered at Visit 2 (Week 0) and Visit 5 (Week 8). Subjects will be randomized to 1 of 4 induction treatment arms (LY3074828 30 mg SC, LY3074828 100 mg SC, LY3074828 300 mg SC, and placebo every 8 weeks [Q8W]) stratified on the basis of previous exposure to biologic therapy for treatment of psoriasis.

Maintenance Period (88 weeks): The Maintenance Period consists of 88 weeks of treatment. At the end of the Induction Period (Week 16), subjects will continue treatment in the Maintenance Period which is intended to explore 1 of 2 treatment strategies through Week 104. All placebo subjects and subjects assigned to treatment with LY3074828 who have a <90% improvement in Psoriasis Area and Severity Index (PASI) from baseline (PASI 90) at Week 16 will receive LY3074828 300 mg SC Q8W during the entire Maintenance Period. Subjects with ≥PASI 90 PRN dosing group) at Week 16 will only be dosed with LY3074828 at the baseline dose level assignment no more frequently than Q8W when disease activity level is <PASI 90, and this will continue until ≥PASI 90 is regained.

Follow-up Period (16 weeks): The Follow-up Period will include a visit every 4 weeks for a total of 16 weeks following Visit 29 to assess subject safety and study drug efficacy.

[Figure 5.1](#) illustrates the study design.

^a Visits will occur every 4 weeks in the Maintenance and Follow-up Periods.
 Abbreviations: PASI = Psoriasis Area and Severity Index; PRN = as needed; Q8W = every 8 weeks.

Figure 5.1. Illustration of study design for Clinical Protocol I6T-MC-AMAF.

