$$(First\ study\ day\ when\ response\ is\ lower\ than\ the\ specified\ level - First\ study\ day\ when\ response\ is\ greater\ than\ or\ equal\ to\ the\ specified\ level + 1) / 7$$

If a patient does not lose response by completion or early discontinuation of the Maintenance Period, the patient will be censored with the censored date defined as the earliest date between the data cutoff for an interim analysis, the study discontinuation date, Maintenance Period end date for non-rescued patients, or the rescue start date.

Time to Recapture of Response in the Maintenance Period After PRN Dosing

Time to recapture of response (for example, PASI 90 or PASI 100) in the Maintenance Period includes only those subjects who lost the specified level of response during the Maintenance Period and is defined in weeks as:

$$(First\ study\ day\ when\ response\ is\ recaptured\ at\ the\ specified\ level - First\ study\ day\ when\ response\ is\ lower\ than\ the\ specified\ level + 1) / 7$$

If a patient does not recapture response by completion or early discontinuation of the Maintenance Period, the patient will be censored with the censored date defined as the earliest date between the data cutoff for an interim analysis, the study discontinuation date, Maintenance Period end date for non-rescued patients, or the rescue start date.

Time to Recapture of Response in the Rescue Period

Time to recapture of response (PASI 50, PASI 90, or PASI 100) in the Rescue Period includes only those subjects who lost the specified level of response during the Maintenance Period and is defined in weeks as:

$$(First\ study\ day\ when\ response\ is\ recaptured\ at\ the\ specified\ level - First\ study\ day\ when\ response\ is\ lower\ than\ the\ specified\ level + 1) / 7$$

If a patient does not recapture response by completion or early discontinuation of the Rescue Period, the patient will be censored with the censored date defined as the earliest date between the data cutoff for an interim analysis, the study discontinuation date, Rescue Period end date, and the start date of the Follow-up Period.

For variables that are not collected at each postbaseline visit, data may exist at visits where the variable was not scheduled to be collected, due to early discontinuation visits. In these situations, data from the early discontinuation visit that do not correspond to the planned

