	Time to first loss of response (PASI 90, PASI 100) for PRN subjects	KM product limit curve; time to loss of response	Maintenance Period Efficacy Population	Maintenance Period

Measure	Variable	Analysis Method (Sections 6.1.3)	Population (Section 6.1.1)	Time Point
	Time to recapture of response (PASI 90, PASI 100) after first loss of response for PRN subjects	KM product limit curve; time to response recapture after first loss of response	Maintenance Period Efficacy Population	Maintenance Period
	Time to recapture of response (PASI 50, PASI 90) after loss of response for rescued subjects	KM product limit curve; time to response recapture after first loss of response	Rescue Period Efficacy Population	Rescue Period
sPGA	sPGA (0,1); sPGA (0)	Logistic regression analysis with NRI	ITT Population	All pairwise comparisons against placebo at all postbaseline visits in Induction Period
		Summary statistics with NRI	Maintenance Period Efficacy Population	All visits in Maintenance Period
		Summary statistics (As observed) or individual trajectory line plot if total number of subjects is too small	Rescue Period Efficacy Population	All visits in Rescue Period
BSA	BSA change from baseline	MMRM; mBOCF ANCOVA	ITT Population	All pairwise comparisons against placebo at all postbaseline visits in Induction Period
		MMRM	Maintenance Period Efficacy Population	All visits in Maintenance Period
PSSI	PSSI percent improvement from baseline (for subjects with scalp psoriasis involvement only); PSSI score (for all subjects)	MMRM; mBOCF ANCOVA	ITT Population	All pairwise comparisons against placebo at all postbaseline visits in Induction Period
		MMRM	Maintenance Period Efficacy Population	All visits in Maintenance Period
	PSSI score = 0 (for all subjects)	Logistic regression analysis with NRI	ITT Population	All pairwise comparisons against placebo at all postbaseline visits in Induction Period
	Summary statistics with NRI	Maintenance Period Efficacy Population	All visits in Maintenance Period	

Measure	Variable	Analysis Method (Sections 6.1.3)	Population (Section 6.1.1)	Time Point
DLQI	DLQI (0,1), DLQI (0)	Logistic regression analysis with NRI	ITT Population	All pairwise comparisons against placebo at all postbaseline visits in Induction Period
		Summary statistics with NRI	Maintenance Period Efficacy Population	All visits in Maintenance Period

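### For PASI 100, the time-to-recapture analysis labelled as following PRN dosing starts at loss of response and requires no PRN dose, so it does not isolate retreatment

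*SAP*

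**What the plan says.** The exploratory objective in SAP 4.3 is "To characterize the ability of retreatment (if applicable) with LY3074828 to regain PASI 100 for subjects who achieve PASI 100 response at Week 16" and who then lose that response during maintenance.

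The analysis serving it is in SAP 6.1.3 under the subheading "Time to Recapture of Response in the Maintenance Period After PRN Dosing". Its entry rule reads: "Time to recapture of response (for example, PASI 90 or PASI 100) in the Maintenance Period includes only those subjects who lost" the named level. The time in weeks is the first study day back at the level, minus the first study day below it, plus 1, divided by 7. A subject who does not regain the level is censored at the earliest applicable date among interim data cutoff, study discontinuation, end of the Maintenance Period and rescue start. SAP Table 6.3 lists the variable as "Time to recapture of response (PASI 90, PASI 100) after first loss of response for PRN subjects".

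The dosing rule is in SAP 5.1: subjects in the PRN group "will only be dosed with LY3074828 at the baseline dose level assignment no more frequently than Q8W when disease activity level is <PASI 90". Protocol 5.4 gives the same trigger. The Schedule of Activities (Protocol 2) has the need for a dose judged at every maintenance visit, 4 weeks apart, and gives no Week 16 dose to subjects at PASI 90 or better.

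SAP 6.9.3 reports the Kaplan-Meier results by PRN arm. It separately summarises the number of PRN doses and the week of the first PRN dose after loss.

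**The concern.** For PASI 100, losing the response and qualifying for a dose are different events. Any residual disease ends PASI 100, whereas a dose needs improvement to fall below 90%. Subjects between the two enter the risk set with no PRN dose given in response to that loss. Three things follow:

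- A return to PASI 100 without a dose is counted as recapture after PRN dosing.
- A subject dosed later carries the undosed wait inside the recapture time.
- A subject who stays in the band is censored as not recaptured, although retreatment was never tried.

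The curve thus mixes fluctuation near clearance with response to a dose. Results are shown by PRN arm, and time spent in the band could differ between 30, 100 and 300 mg, so a difference between curves need not reflect retreatment. SAP 5.2 says the PRN results will support the Phase 3 maintenance dosing strategy, so the curve may be read as evidence on retreatment.

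**Working it through.** The documents give no figure for this analysis, so there is none to reproduce. The check applies the SAP's own definitions.

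**Step 1. The band with loss but no dose.** Inputs: PASI moves in steps of 0.1, PASI 100 is 100% improvement and PASI 90 is at least 90% (SAP Table 6.2); the minimum baseline PASI is 12 (Protocol 6.1). With baseline *b*, PASI 100 is lost at any score above 0, and a dose needs a score above 0.1 × *b*.

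| Baseline PASI | PASI 100 lost from | Lost, no dose | Dose trigger |
|---|---|---|---|
| 12 | 0.1 (11.9/12 = 99.2% improvement) | 0.1 to 1.2 | 1.3 or more |
| 20 (illustrative) | 0.1 (19.9/20 = 99.5% improvement) | 0.1 to 2.0 | 2.1 or more |

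**Step 2. The formula on the visit grid.** Visit days come from the Schedule of Activities: Week 20 = day 140, Week 24 = 168, Week 36 = 252, Week 44 = 308, Week 104 = 728. In all cases PASI 100 is lost at Week 20.

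- Dosed at Week 36, clear at Week 44. SAP time: (308 − 140 + 1)/7 = 24.14 weeks. From the dose: (308 − 252 + 1)/7 = 8.14 weeks. The undosed part is (252 − 140)/7 = 16 weeks.
- Never dosed, clear at Week 24. SAP time: (168 − 140 + 1)/7 = 4.14 weeks, counted as an event.
- In the band until Week 104. Censored after (728 − 140)/7 = 84 undosed weeks.

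If the dose-to-clearance interval is held at 8 weeks and only the dose visit moves, the SAP time is 8.14, 12.14, 24.14 or 48.14 weeks for a dose at Week 20, 24, 36 or 60. The time from the dose is 8.14 in all four.

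**Step 3. PASI 90 for comparison.** The day PASI 90 is first lost is also the day the dosing trigger is met. The last induction dose was at Week 8, so the 8-week minimum interval does not delay a dose at Week 20 or later. Time zero and the first PRN dose coincide, and the problem does not arise.

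**Step 4. How large it could be.** The documents give neither a PASI 100 response rate nor a rate of loss, so only an assumed range is possible. A simulation of 40,000 subjects on 4-weekly visits from Week 20 to Week 104 used three states: clear (PASI 100), band (PASI 90 to <100) and low (<PASI 90, dosed). All subjects start clear. Rescue and dropout are ignored. After a dose, the chance per visit of moving from low to clear is 0.2 and from low to band 0.4 throughout. All transition rates are assumptions.

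| Clear→band, clear→low, band→clear, band→low (per visit) | No dose before recapture or end of period, among losers of PASI 100 | Recaptures without a dose | Counted time that is undosed |
|---|---|---|---|
| 0.05, 0.10, 0.10, 0.50 | 5.7% | 6.1% | 9.6% |
| 0.10, 0.05, 0.15, 0.25 | 25.5% | 26.7% | 30.4% |
| 0.15, 0.02, 0.25, 0.10 | 63.5% | 64.3% | 61.9% |

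**The case against.** The best defence is that the formula does what most of its labels say. Table 6.3 and SAP 6.9.3 describe recapture after loss of response; only the subheading in 6.1.3 mentions PRN dosing, and it may be there to separate this analysis from the Rescue Period one that follows. Time from loss is also a legitimate summary of the PRN strategy, in which withholding a dose between PASI 90 and PASI 100 is part of the strategy. The separate summary of the week of first PRN dose shows some of the delay. A curve restricted to dosed subjects has its own selection, because it keeps only those who fell below PASI 90.

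Much of this stands. It is a reason to keep the time-from-loss curve and relabel it, and to state the selection in any dosed-only curve. It does not answer the objective in SAP 4.3, which names retreatment. The dose summary changes neither who enters, nor when the clock starts, nor what counts as an event, and it does not separate dosed from undosed returns.

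A reader might infer that the curve contains untreated subjects. The documents do not support that: PRN subjects were assigned active drug at Weeks 0 and 8. What is missing is a PRN dose given in response to the loss. A reader might also extend the point to PASI 90, which Step 3 rules out for first loss.

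**Conclusion.** The point holds for PASI 100 only. As written, the analysis measures time to regain PASI 100 after losing it, with or without a dose, and so does not isolate what retreatment achieves. This follows from the definitions and needs no assumption.

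The size is unknown. The 5.7% to 63.5% range for subjects with no dose depends entirely on assumed rates, so a reader should not infer that most of the risk set is undosed. Nor is there a fixed direction: quick undosed returns shorten recapture, while undosed waiting and censoring in the band push it the other way.

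Consequences are limited. The objective is exploratory, the analysis is descriptive, and no primary or secondary result depends on it. The correction is worth making because it is cheap and the PRN results are intended for Phase 3 planning.

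**What to change.** In SAP 6.1.3 and Table 6.3:

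1. Keep the time-from-loss curve for PASI 100, but relabel it *time to regain PASI 100 after first loss*. Report returns with and without an intervening PRN dose separately.
2. For the retreatment objective, add time from the first PRN dose given while PASI 100 is lost to the first later visit at PASI 100, among subjects who received such a dose. The existing censoring dates can be kept.
3. State a rule for subjects who return undosed, lose PASI 100 again and are then dosed. One option is to count the undosed return in the first analysis and let the subject enter the second at the first PRN dose.
4. Note beside the second analysis that it describes the subset who fell below PASI 90.

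The cost is SAP wording and a little more analysis work. PASI is assessed at every maintenance visit and Protocol 7.2.1 already has dose times recorded, so no new data are needed. No change to the dosing rule is implied.

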### 7.8.2. Special Treatment Considerations

Subjects in the maintenance PRN dosing arm may receive blinded rescue treatment with 300 mg Q8W. Rescue treatment may occur if not regaining a PASI  $\geq 90$  after 3 consecutive doses of retreatment or if a subject is below a PASI 50 following 1 retreatment dose. A subject starting rescue treatment will remain on that regimen through the end of the study regardless of any subsequent changes in PASI score.

All biological agents carry the risk of an injection site and/or hypersensitivity general reaction. Therefore all subjects should be closely monitored for signs or symptoms that could result from such reactions. Sites should have appropriately trained medical staff and appropriate medical equipment available when subjects are receiving study drug. If a subject experiences an acute hypersensitivity reaction after an injection of study drug, he or she should receive appropriate supportive care.

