5.2. Determination of Sample Size

Approximately 200 subjects will be randomized at a 1:1:1:1 ratio in the blinded induction dosing period to LY3074828 30 mg, 100 mg, 300 mg, and placebo (50 subjects per dosing regimen, respectively). Randomization will be stratified by prior exposure to biologic therapy for psoriasis (yes/no).

Assuming 60% and 3% PASI 90 response rates at 16 weeks for LY3074828 and placebo, respectively, pairwise comparisons to placebo have over 99% power using a 2-sided Fisher's exact test at the 0.05 significance level, with no adjustment for multiple comparisons.

As results for PRN dose arms in the Maintenance Period will support the maintenance dosing strategy in Phase 3 planning, a reasonable total number of subjects who completed 1-3 visits in the Maintenance Period (Week 20 to Week 28) will be needed. Based on study simulations under the treatment effect scenario outlined above, approximately 49 subjects (9 on 30 mg, 18 on 100 mg, 22 on 300 mg PRN arms) will have completed the Week 20 visit at the time of the primary endpoint datalock.

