6.1.2. Definitions

6.1.2.1. Study Time Intervals

Induction Period

All subjects who were randomized to the study are considered as entering the Induction Period.

The start of the Induction Period is defined as the date of first injection following randomization. For subjects who were randomized but not dosed, the Induction Period starts at the randomization date.

The end of the Induction Period is defined as the date of PASI measurement at Week 16, or the early termination date if subjects discontinued from study prior to or at Week 16, or Day 117, whichever comes first.

Maintenance Period

All subjects who had Week 16 visit with PASI measurement (except the ones discontinued the study at Week 16) are considered to have entered the Maintenance Period.

The start of the Maintenance Period is defined as the same date as end of the Induction Period, which is the date of PASI measurement at Week 16.

The end of the Maintenance Period is defined as the visit date at Week 104, or the date when the subjects received rescue treatment, or the early termination date if subjects discontinued from study prior to or at Week 104, whichever comes first.

Rescue Period

All subjects in PRN groups who received at least 1 dose of rescue treatment are considered to have entered the Rescue Period, and will be included in the Rescue Period analysis population.

The start of the Rescue Period is defined as the date the patient received the first dose of rescue treatment.

The end of the Rescue Period is defined as the visit date at Week 104, or early termination date if subjects discontinued from study prior to or at Week 104, whichever comes first.

Follow-up Period

All subjects who had Visit 29 are considered to have entered the Follow-up Period, and will be included in the Follow-up Period analysis population.

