6.3. Handling of Dropouts or Missing Data

6.3.1. Non-Responder Imputation (NRI)

Analysis of categorical efficacy and health outcome variables will be assessed using a NRI method. Subjects will be considered a non-responder for the NRI analysis if they do not meet the clinical response criteria or have missing clinical response data at the analysis time point. Randomized subjects without at least 1 postbaseline observation will also be defined as non-responders for the NRI analysis.

Due to the design, PRN subjects who got rescued will get a different treatment (300 mg LY SC Q8W), therefore the subsequent visits following the first dose of rescue treatment will be defined as non-responders in the analysis for the Maintenance Period.

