6.9.3. Exploratory Analyses

Analyses of body surface area (BSA) and Psoriasis Scalp Severity Index (PSSI) exploratory outcomes are described in [Table 6.2](#) and [Table 6.3](#).

The Kaplan-Meier product limit method will be used to estimate the survival curves for the Maintenance and Rescue Period time-to-event variables (time to loss of response for subjects in as needed (PRN) arm, time to response recapture after loss of response for subjects who lost response in PRN arm). Time to event analyses will be summarized by PRN treatment arms.

Summary of PRN doses, including total number of PRN doses given and week of first PRN dose given after loss of response, will be summarized by PRN treatment arms.

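### Censoring exploratory PRN recapture times at rescue makes 1 minus Kaplan-Meier overstate recapture on PRN whenever rescues precede later recaptures

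*SAP*

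**What the plan says.** - **Endpoint and censoring.** SAP 6.1.3 measures Maintenance Period recapture in PRN subjects who have lost the given PASI level. "If a patient does not recapture response by completion or early discontinuation of the Maintenance Period, the patient will be censored". The censoring date is the earliest of the interim data cutoff, the study discontinuation date, "Maintenance Period end date for non-rescued patients, or the rescue start date".
- **Estimator.** SAP 6.1.3 and Table 6.3 specify Kaplan-Meier curves with medians, and SAP 6.9.3 adds: "Time to event analyses will be summarized by PRN treatment arms". No competing-event, rescue-as-failure or sensitivity version is given for this endpoint.
- **Who is rescued.** Under Protocol 7.8.2 a PRN subject may be rescued if PASI 90 is not regained "after 3 consecutive doses of retreatment or if a subject is below a PASI 50 following 1 retreatment dose". A rescued subject stays on 300 mg Q8W to the end of the study. PRN doses are given "no more frequently than Q8W when disease activity level is <PASI 90" (SAP 5.1).
- **Same event, by-visit analysis.** SAP 6.3.1 says that "the subsequent visits following the first dose of rescue treatment will be defined as non-responders in the analysis for the Maintenance Period".
- **Status.** The recapture objectives are exploratory (SAP 4.3). SAP 5.2 opens its reasoning on PRN numbers with: "As results for PRN dose arms in the Maintenance Period will support the maintenance dosing strategy in Phase 3 planning".

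**The concern.** Kaplan-Meier treats a censored subject as having the same later chance of the event as those still at risk, and shares that subject's probability among them. A rescued subject has left PRN dosing permanently, so recapture on PRN is no longer possible. Censoring at rescue therefore credits PRN with recaptures that cannot happen.

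The curves are meant to describe how well retreatment regains response, by PRN dose arm. With similar rescue patterns, an arm with more failures is flattered more and a difference between doses is compressed. The non-responder rule in SAP 6.3.1 does not repair this: it describes all PRN subjects at a visit, not recapture among those who lost response.

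**Working it through.** The plan states no figure for this endpoint, so there is none to reproduce. The size has to be illustrated.

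**Two targets**
- A: the proportion who recapture on PRN before rescue. This is the cumulative incidence with rescue as a competing event; without other censoring it is the sum of the recapture masses d_j.
- B: the proportion who would recapture if no one were rescued.
- The planned estimate is 1 − Π(1 − d_j/n_j), where n_j excludes rescued subjects.

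**Inputs from the documents:** the censoring rule (SAP 6.1.3), the two triggers (Protocol 7.8.2), Q8W minimum spacing (SAP 5.1) and 4-weekly visits.

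**Assumptions, not in the documents:** recaptures equally likely at 4, 8, 12, 16 and 20 weeks after loss; 10, 20, 30 or 40% never recapture on PRN; 50, 80 or 100% of these are rescued (rescue is optional); early rescue at 8 weeks, after one dose; other rescue at 24 weeks, after doses at 0, 8 and 16 weeks. All rescued subjects come from the never-recapture group.

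**Worked case: 40% never recapture, 80% of them rescued, half of these early**
- Recapture mass per visit: 0.60/5 = 0.12. Rescued at week 8: 0.40 × 0.80 × 0.50 = 0.16.
- Survival: (1 − 0.12/1)(1 − 0.12/0.88)(1 − 0.12/0.60)(1 − 0.12/0.48)(1 − 0.12/0.36) = 0.304.
- 1 − KM = 0.696. Targets A and B are both 5 × 0.12 = 0.60, so the overstatement is about 10 points.

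**Range at 24 weeks, half of rescues early**

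| Never recapture | 10% | 20% | 30% | 40% |
|---|---|---|---|---|
| Target | 0.90 | 0.80 | 0.70 | 0.60 |
| 1 − KM, 50% rescued | 0.922 | 0.838 | 0.749 | 0.655 |
| 1 − KM, 80% rescued | 0.936 | 0.864 | 0.784 | 0.696 |
| 1 − KM, 100% rescued | 0.946 | 0.883 | 0.811 | 0.729 |

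Over early shares of 0 to 75%, the overstatement is 0–9, 0–17 and 0–24 points for 50, 80 and 100% rescued, and 0–25 if early rescue could come at 4 weeks (maximum 0.848 against 0.60). It is zero when all rescue follows the last recapture.

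**Same case with rescue unrelated to prognosis**
- At week 8, 0.24 have recaptured and 0.76 remain at risk. Remove 0.16 at random, leaving 0.60.
- Later recaptures on PRN: 0.36 × 0.60/0.76 = 0.284. Target A = 0.24 + 0.284 = 0.52.
- Target B is 0.60 and Kaplan-Meier returns 0.60. It is unbiased for B but 8 points above A.

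**Second model** (assumed recapture chance per visit 0.35 for good and 0.03 for poor recapturers, 20–40% poor)
- Half of the unrecaptured poor recapturers rescued at week 8: Kaplan-Meier at week 24 exceeds A by 6–10 points and B by 5–8.
- All of them rescued at week 8: it exceeds A by 16–31 and B by 13–27.
- Three-dose rescue only: no difference through week 24. If a random half is then rescued at each 8-week point, Kaplan-Meier at week 48 equals B but exceeds A by 5–6 points (0.788 against 0.729 with 30% poor).

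**Medians.** In the main illustration the median moves by zero or one 4-week visit. With 80% rescued and half early it is 12/12/16/16 weeks by Kaplan-Meier and 12/16/16/20 by cumulative incidence. In an invented 20-patient arm with recaptures only at 8-week points, it moved from 24 to 32 weeks.

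**Dose contrast.** Failure of 10% in one arm and 40% in another is a 30-point gap. With equal rescue patterns and half early, Kaplan-Meier shows 0.922 − 0.655 = 27, 0.936 − 0.696 = 24 and 0.946 − 0.729 = 22 points for 50, 80 and 100% rescued.

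**The case against.** - **Not having recaptured is not in itself informative.** Everyone still at risk has not yet recaptured. A no-rescue curve is biased only if rescued subjects have a different future chance. This stands: a reader might infer that both triggers bias Kaplan-Meier for that target, but only the below-PASI-50 trigger plausibly selects on prognosis. It does not rescue the planned curve as an estimate of recapture before rescue, and the SAP does not state that the no-rescue quantity is what it wants.
- **The sizes are built in.** The main illustration assumes that every rescued subject would never have recaptured. This stands; neither model gives a bound, and both start at zero.
- **Rescue does not mean the same in each arm.** In the 300 mg arm, rescue uses the same dose level as PRN; in the 30 and 100 mg arms it raises the dose. This stands as a caution for reading any cumulative incidence by arm.
- **Precision is low.** Only subjects who lost response are analysed. At the SAP 5.2 planning rate, about 0.60 × 50 = 30 per arm enter PRN. If half lose response (assumed), n = 15 and the binomial standard error is √(0.60 × 0.40/15) = 0.126. A 10-point overstatement is then smaller than one standard error, though it is systematic and does not average out.
- **Phase 3 relevance.** A reader might infer that the Phase 3 decision rests on these curves. SAP 5.2 speaks of subjects with one to three Maintenance visits (Weeks 20–28). With loss at Week 20 and the timing assumed here, early rescue falls at Week 28 and the 24-week result at Week 44.
- **Rescue Period clock.** A reader might also infer that timing Rescue Period recapture from first loss is an error, because "The start of the Rescue Period is defined as the date the patient received the first dose of rescue treatment". Table 6.3 labels that analysis as time after first loss, and rescue visits are also summarised as observed, so the documents do not support calling it a mistake.

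**Conclusion.** The point holds and is minor. As an estimate of recapture on the assigned PRN regimen before rescue, the planned 1 minus Kaplan-Meier is too high whenever rescue precedes later recaptures. As an estimate of recapture without rescue, it is too high only if rescue selects poor prognosis.

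The direction follows from the two documents; the size does not. It is 0 to about 25 points in the main illustration and up to 31 at the extreme of the second model, and any single figure would be an assumption. The planned medians move little in most scenarios. The handling of rescue is also inconsistent with SAP 6.3.1. The analyses are exploratory and descriptive, and the Week 16 primary analysis is untouched.

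**What to change.** In SAP 6.1.3, for Maintenance Period recapture:

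1. State the estimand as recapture on the assigned PRN regimen before rescue.
2. Report the cumulative incidence of recapture (Aalen-Johansen) by PRN arm, with rescue start as a competing event. Dropout, period end and interim cutoff stay as censoring.
3. Report the number rescued in each arm, by trigger.
4. Keep the planned Kaplan-Meier curve as a supplement, labelled as a no-rescue estimate that assumes rescue is unrelated to prognosis.
5. Note beside the output that rescue in the 300 mg arm uses the same dose level as PRN, so the competing event differs in meaning between arms.

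Optional, not a correction: add a Rescue Period summary timed from the first rescue dose. For PASI 90 recapture 8 weeks after that dose, the planned clock reads (16 × 7 + 1)/7 = 16.1 weeks if rescue came 8 weeks after loss and (32 × 7 + 1)/7 = 32.1 if it came 24 weeks after loss, against (8 × 7 + 1)/7 = 8.1 from rescue in both.

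The cost is SAP wording and programming, with no new data and no change to the rescue rule. Recapture may look less favourable, and the new curve needs a short explanation.
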